14.4 PUBLICATION AND DATA SHARING POLICY.....	50
15 CONFLICT OF INTEREST POLICY	50
16 LITERATURE REFERENCES	50
APPENDICES	50
APPENDIX A. PATIENT GLOBAL IMPRESSION OF CHANGE (PGIC)	50
APPENDIX B. ECOG PERFORMANCE STATUS	50
APPENDIX C. MPN SYMPTOMS ASSESSMENT FORM.....	51
APPENDIX D. MODERATE/STRONG INDUCERS/INHIBITORS OF CYP3A4	51
APPENDIX E. WHO DIAGNOSTIC CRITERIA FOR MDS/MPNs	52
APPENDIX F. PROPOSED MDS/MPN RESPONSE CRITERIA.....	55
APPENDIX G. CORRELATIVE WORKSHEET	56

r

LIST OF ABBREVIATIONS

AE	Adverse Event
ALT	Alanine Aminotransferase
AST	Aspartate Aminotransferase
BUN	Blood Urea Nitrogen
CFR	Code of Federal Regulations
CMML	Chronic Myelomonocytic Leukemia
CMP	Clinical Metabolic Panel
CNL	Chronic Neutrophilic Leukemia
CRF	Case Report Form
CRP	C-reactive protein
DSMB	Data Safety Monitoring Board
eCRF	Electronic Case Report Forms
FDA	Food and Drug Administration
FLT3	FMS-like tyrosine kinase 3
GCP	Good Clinical Practice
HIPAA	Health Insurance Portability and Accountability Act
IB	Investigator's Brochure
ICH	International Conference on Harmonisation
ICH E6	International Conference on Harmonisation Guidance for Industry, Good Clinical Practice: Consolidated Guidance
IND	Investigational New Drug Application
IRB	Investigational Review Board
ISO	International Organization for Standardization
IWG-MRT	International Working Group – Myeloproliferative Neoplasms Research and Treatment
JAK2	Janus-associated kinase-2
LDH	Lactate Dehydrogenase
MDS/MPN	Myelodysplastic Syndrome/Myeloproliferative Neoplasm
MF	Myelofibrosis
MPN	Myeloproliferative Neoplasm
OHRP	Office for Human Research Protections
ORR	Overall Response Rate
OS	Overall Survival
PET-MF	Post-Essential Thrombocythemia Myelofibrosis
PFS	Progression Free Survival
PGIC	Patient Global Impression of Change
PI	Principal Investigator
PMF	Primary Myelofibrosis
PPV-MF	Post-Polycythemia Vera Myelofibrosis
RR	Response rate
SAE	Serious Adverse Event
SAF	Symptom Assessment Form
SAP	Statistical Analysis Plan
SMC	Safety Monitoring Committee
SOP	Standard Operating Procedure
SVR	Spleen volume reduction
TSS	Total Symptom Score
UP	Unanticipated Problem

US	United States
----	---------------

STATEMENT OF COMPLIANCE

The trial will be conducted in accordance with the ICH E6, the Code of Federal Regulations on the Protection of Human Patients (45 CFR Part 46). The Principal Investigator will assure that no deviation from, or changes to the protocol will take place without prior agreement from the sponsor and documented approval from the Institutional Review Board, except where necessary to eliminate an immediate hazard(s) to the trial participants. All personnel involved in the conduct of this study have completed Human Subjects Protection Training.

I agree to ensure that all staff members involved in the conduct of this study are informed of their obligation to meet the above commitments.

Principal Investigator: [name]
Print/Type Name

Signed: _____ Date: _____

STUDY SUMMARY

- Title:** A Phase 2 Study of Fedratinib in Myelodysplastic /Myeloproliferative Neoplasms (MDS/MPNs) and Chronic Neutrophilic Leukemia (CNL)
- Objectives:**
- Primary Objective:
- 1.) To evaluate the efficacy of fedratinib in patients with MDS/MPNs and CNL
- Important Secondary Objectives:
- 1.) To evaluate the safety and tolerability of fedratinib in MDS/MPNs and CNL.
 - 2.) To evaluate the effect of fedratinib in MDS/MPNs and CNL on patient-reported outcomes.
- Endpoint**
- Primary Efficacy Endpoint
- 1.) Proportion of patients achieving a clinical response from baseline to week 24 as defined as complete remission (CR), partial remission (PR), or clinical benefit (CB) per Modified MDS/MPN IWG Proposed Response Criteria¹
- Safety and Tolerability Endpoints
- 1.) Frequency, duration, and severity of adverse events (AE) will be determined by performing physical exams, and evaluating changes in vital signs, serum chemistry, hematology and urinalysis results using CTCAE version 5.0.
 - 2.) Proportion of patients experiencing grade ≥ 3 AE as defined by CTCAE v.5.0
- Important Secondary Efficacy Endpoints:
- a. Proportion of patients achieving spleen response at week 12 in patients with baseline splenomegaly.
 - b. Proportion of patients achieving spleen response at week 24 in patients with baseline splenomegaly.
 - c. Proportion of patients who have a 50% reduction in MPN-SAF TSS from baseline to week 12 in patients with baseline TSS ≥ 10
 - d. Proportion of patients who have a 50% reduction in MPN-SAF TSS from baseline to week 24 in patients with baseline TSS ≥ 10
 - e. Change in TSS from baseline to week 12 in patients with baseline TSS ≥ 10
 - f. Change in TSS from baseline to week 24 in patients with baseline TSS ≥ 10
 - g. Change in TSS from baseline to time of best response in patients with baseline TSS ≥ 10
 - h. Patient's global impression of change (PGIC) at week 12
 - i. PGIC at week 24

Sample Size: Total Patient Population: 25

Population: Patients \geq 18 years old with MDS/MPNs or CNL.

Phase: 2

[figure not shown]
Number of Sites enrolling: 4

Description of Study Agent: Fedratinib 400 mg PO daily

Study Duration: 36 months

Participant Duration: 24 months

SCHEMATIC OF STUDY DESIGN

2 INTRODUCTION: BACKGROUND INFORMATION AND SCIENTIFIC RATIONALE

2.1 BACKGROUND INFORMATION

Disease Background

Myelodysplastic/Myeloproliferative Neoplasms (MDS/MPNs) and chronic neutrophilic leukemia (CNL) are heterogeneous myeloid malignancies that are characterized by proliferative features, bone marrow dysfunction, complex molecular features, and poor outcomes.² Clinically and genetically, these diseases have significant overlap and are better viewed as a continuum of disease rather than distinct disease entities.² Treatment is typically symptom-directed and based on extrapolation from other, related disease entities. Therapeutic options have traditionally included cytoreductive agents such as hydroxyurea and hypomethylating agents such as azacitidine and decitabine.³⁻⁶ With the exception of azacitidine and decitabine for CMML, there are currently no FDA-approved therapies for these indications. Allogeneic hematopoietic cell transplant (AHCT) offers a curative option for some patients, but the majority of patients are not eligible for this procedure due to age, comorbidities, or lack of a suitable donor.⁷⁻¹³ Clinical trials represent a preferred option, but these diagnoses are often excluded from clinical trials that specifically enroll myelodysplastic syndrome (MDS) or MPN patients.¹⁴

Upregulation of the Janus kinase (JAK)/Signal transducer and activator of transcription (STAT) pathway is a hallmark of MPNs. This results in cell proliferation, inhibition of cell death and clonal expansion of myeloproliferative malignant cells.¹⁵ JAK2 inhibitors that downregulate the JAK/STAT pathway can be expected to reduce cell proliferation and induce malignant cell killing in MPN patients. To that end, JAK2 inhibitors have been shown to improve disease-related symptoms and splenomegaly in patients with MF.¹⁶⁻¹⁹

Preclinical work has shown that MDS/MPNs feature GM-CSF hypersensitivity that can be abrogated with JAK

inhibition.²⁰ Additionally, driver mutations involving the JAK/STAT pathway are frequently present in MDS/MPNs and CNL.² Several small studies assessing JAK inhibition in MDS/MPNs with ruxolitinib have shown activity in this setting.²¹⁻²³

Study Agent Background

Fedratinib, an oral kinase inhibitor with activity against wild type and mutationally activated Janus Associated Kinase 2 (JAK2) and FMS-like tyrosine kinase 3 (FLT3), was recently approved in the United States and is indicated for the treatment of adult patients with intermediate-2 or high-risk primary or secondary (post-polycythemia vera or post-essential thrombocythemia) myelofibrosis (MF). The registration of fedratinib was supported by data from Study EFC12153 (JAKARTA), a randomized, placebo-controlled, Phase 3 study in patients with intermediate-2 or high-risk PMF, post-PV MF, or post-ET MF with splenomegaly.

JAKARTA met its primary endpoint, with 36.5% of patients in the 400 mg fedratinib arm compared with 1.0% of patients in the placebo arm achieving $\geq 35\%$ SVR at the end of cycle 6 confirmed 4 weeks later ($p < 0.0001$). When response was assessed at the end of cycle 6, as per IWG MRT criteria, 46.9% of patients treated with fedratinib 400 mg achieved $\geq 35\%$ spleen volume reduction (SVR); the rate remained at 1% for patients in the placebo arm ($p < 0.0001$). Kaplan-Meier estimate for median duration of spleen response was 18.2 months for patients in the fedratinib 400 mg arm and suggest durable response. The study also met its key secondary endpoint by demonstrating clinically meaningful and statistically significant superiority of fedratinib 400 mg over placebo for symptom response rate (RR). Symptom RR is defined as $\geq 50\%$ reduction in total symptoms score (TSS) and was 40.4% in the fedratinib 400 mg arm and 8.6% in the placebo arm; the difference was statistically significant ($p < 0.0001$). Further, reductions in all individual symptoms from the modified MF-SAF contributed to the improvement observed in patients treated with fedratinib.

Based on these data, the author believes there is rationale for further study of fedratinib in MDS/MPNs and CNL.

2.2 RATIONALE

MDS/MPNs and CNL comprise a group of molecular complex, heterogenous, myeloid malignancies that have limited treatment options and poor prognoses. Patients frequently exhibit proliferative features of leukocytosis, splenomegaly, and constitutional symptoms that negatively impact quality of life. Moreover, these diseases frequently progress to acute myeloid leukemia and overall survival is estimated between 1-3 years.²⁴⁻²⁶ AHCT offers the only curative approach, but is associated with significant morbidity and mortality and most patients are not eligible due to comorbidities, functional status or lack of a suitable donor.

JAK/STAT inhibition offers a promising therapeutic approach for patients with MDS/MPNs and CNL. Preclinical data in MDS/MPNs have shown these cells to exhibit GM-CSF hypersensitivity that signals through the JAK/STAT pathway and can be abrogated by JAK2 inhibition.²⁰ Moreover, many of these patients harbor driver mutations that signal through the JAK/STAT pathway.² Small studies using the JAK1/2 inhibitor ruxolitinib in CMML, aCML and CNL have demonstrated promising activity, and large studies using ruxolitinib and fedratinib in MF have led to regulatory approval based on the ability for these agents to improve disease-related symptoms and reduce spleen size.^{16-19,22,27}

Fedratinib is a selective JAK2 inhibitor with a unique kinase inhibition profile. In addition to inhibition JAK2 in its active and mutated form, fedratinib has activity against FLT3 – a protein implicated in proliferative myeloid malignancies. Fedratinib showed significant activity in MF patients who were intolerant or resistant to ruxolitinib – a group of patients known to have molecularly complex disease and extremely poor outcomes.^{17,28,29}

Based on this data, we believe that fedratinib will have significant activity in MDS/MPNs and CNL. To further investigate this, we are proposing an open-label, phase 2 study to evaluate the safety and efficacy of fedratinib in this setting. Fedratinib will be given orally at 400 mg daily which is the recommended dose based on its label for patients with higher-risk MF.

Patients with a diagnosis of MDS/MPN-U, aCML, MDS-MPN-RS-T, and CNL will be enrolled. A modified Simon's minimax 2-stage approach will be used, wherein an interim analysis will be performed after nine patients are evaluable for response to assess for futility. The primary endpoint of the study will be the proportion of patients achieving an objective clinical response at week 24. This endpoint is consistent with typical endpoints for early phase trials in MPN and MDS/MPN and the timeframe is consistent with that which has been utilized in prior studies of JAK inhibitors.

2.3 POTENTIAL RISKS AND BENEFITS

2.3.1 KNOWN POTENTIAL RISKS

According to the US fedratinib package insert, fedratinib has been used to treat 608 patients with either MPNs or solid tumors. The safety profile of the drug is consistent across studies with the most common adverse events (AEs) being hematologic and gastrointestinal (GI). The most common hematologic AEs are anemia and thrombocytopenia. These events can be managed by dose modification, including dose interruption and other supportive treatments. The most common GI events are diarrhea, nausea, and vomiting. Gastrointestinal events are generally Grade 1 to 2, but Grade 3 to 4 events have occurred and have led to discontinuation of treatment. These events commonly occur at the highest frequency in the first two cycles. Prophylactic anti-emetic therapy (e.g., 5-HT₃ receptor antagonists) during fedratinib treatment should be considered. Diarrhea should be treated with anti-diarrheal medications promptly at the first onset of symptoms. Common laboratory findings include increased alanine aminotransferase (ALT), increased aspartate aminotransferase (AST), increased amylase, increased lipase, and creatinine increased. These events are primarily asymptomatic and Grade 1 to 2 in severity. Recommendations for monitoring and dose modifications are included in the protocol.

Serious and fatal encephalopathy, including Wernicke's, was reported in patients taking fedratinib. Serious cases were reported in 1.3% (8/608) of patients treated with fedratinib in clinical trials and 0.16% (1/608) of cases were fatal.

Seven out of the 8 patients were taking fedratinib at 500mg daily prior to the onset of neurologic findings and had predisposing factors such as malnutrition, gastrointestinal adverse events, and other risk factors that could lead to thiamine deficiency. This dose will not be assessed in the current study. Most events resolved with some residual neurological symptoms including memory loss, cognitive impairment, and dizziness. In a solid tumor study, one patient with head and neck cancer, brain metastasis, difficulty eating and weight loss had a fatal outcome.

Despite these potential risks, we believe the investigation of fedratinib in patients with MDS/MPN and CNL is worth pursuing since these diseases have poor prognoses, lack treatment options, and the preclinical and clinical evidence suggests patients have a high potential to benefit.

2.3.2 KNOWN POTENTIAL BENEFITS

Fedratinib was approved in the US in 2019 and is indicated for the treatment of adult patients with intermediate-2 or high-risk primary or secondary (post-polycythemia vera or post-essential thrombocythemia) myelofibrosis (MF). The registration of fedratinib was supported by data from Study EFC12153 (JAKARTA), a randomized, placebo-controlled, Phase 3 study in patients with intermediate-2 or high-risk PMF, post-PV MF, or post-ET MF with splenomegaly.¹⁶

In this study, fedratinib was shown to produce spleen responses in 36.5% of the patients treated with a 400 mg daily dose compared to 1% of those patients in the placebo arm. Spleen response lasted for 18.2 months suggesting potential for durable responses. The study also met its key secondary endpoint by producing a symptom response ($\geq 50\%$ reduction in total symptoms score) in 40% of patients compared to only 9% of patients who achieved a symptom response on the placebo arm.

In an exploratory analysis of two phase I studies of fedratinib in MF, improvement or stabilization of bone marrow fibrosis was seen in 83% of patients at cycle 6.³⁰

Based on the available data, patients treated with fedratinib have the potential to achieve reduction in spleen size, improvement in disease-related symptoms, patient-reported outcomes, and may experience stability or improvement in bone marrow fibrosis.

3 OBJECTIVES AND PURPOSE

The primary objective of this study is to evaluate the efficacy of fedratinib in patients with MDS/MPNs and CNL. Formal response assessment will be performed at week 24 using information from bone marrow biopsy, spleen imaging, hematologic laboratory values and physical exam. Responses will be determined based upon the Modified MDS/MPN IWG Proposed Response Criteria.¹

We will also evaluate the safety and tolerability of fedratinib in patients with MDS/MPNs and CNL. Safety and tolerability will be assessed in all patients receiving at least one dose of the study drug. CTCAE version 5.0 will be used to detail the scope and severity of AEs.

Secondary objectives will be to evaluate the efficacy of fedratinib in MDS/MPNs and CNL as it pertains to spleen size and patient-reported outcomes (PRO). Patients will have spleen size assessments performed at baseline, week 12, week 24 and every 24 weeks thereafter up to 96 weeks. To evaluate PROs, patients will complete validated questionnaires that assess disease-related symptoms and their global impression of change while on the study agent.

From an exploratory state, we will further assess the efficacy of fedratinib in patients with MDS/MPN and CNL by measuring progression-free survival (PFS), overall survival (OS), and duration of response. Additional exploratory objectives will aim to correlate the presence or lack of a response with the presence and quantity of specific genetic mutations and, when feasible, with matched PDX mouse models. Serial single-cell sequencing will also be used to analyze clonal dynamics at a single-cell level in response to JAK inhibition with fedratinib.

4 STUDY DESIGN AND ENDPOINTS

4.1 DESCRIPTION OF THE STUDY DESIGN

This is an open-label, multi-center, phase 2 study of fedratinib in MDS/MPN and CNL. Approximately 25 patients will be enrolled at 4 US sites. The study will be enrolled via modified Simon's minimax 2-stage approach wherein an interim efficacy analysis will be performed after 9 patients have either completed 24 weeks of treatment or come off study treatment to assess for futility. This will determine whether the remainder of the planned study population will be enrolled.

4.2 STUDY ENDPOINTS

4.2.1 PRIMARY ENDPOINT

- To estimate the response rate of fedratinib in MDS/MPN and CNL, we will measure the proportion of patients achieving a clinical response from baseline to week 24 as defined by CR, PR, or CB by Modified MDS/MPN IWG Proposed Response Criteria.¹ This is a standard endpoint to measure drug activity in phase 2 MPN trials.

4.2.2 SECONDARY ENDPOINTS

- To evaluate the safety and tolerability of fedratinib in MDS/MPNs and CNL we will:
 - Measure the frequency, duration, and severity of AEs per CTCAE v.5.0 using information from physical exams, evaluation of changes in vital signs, serum chemistry, and hematology.
 - Determine the proportion of patients experiencing grade ≥ 3 AE as defined by CTCAE v.5.0
- To evaluate the efficacy of fedratinib on splenomegaly in MDS/MPNs and CNL we will:
 - Determine the proportion of patients who have a spleen response at week 12 as per Modified MDS/MPN IWG Proposed Response Criteria or demonstration of $\geq 35\%$ spleen volume reduction.
 - Determine the proportion of patients who have a spleen response at week 24 as per Modified MDS/MPN IWG Proposed Response Criteria or demonstration of $\geq 35\%$ spleen volume reduction.
- To evaluate the efficacy of fedratinib on patient-reported outcomes in MDS/MPNs and CNL we will:
 - Determine the proportion of patients who have a 50% reduction in MPN-SAF TSS from baseline to week 12 in patients with baseline TSS ≥ 10
 - Determine the proportion of patients who have a 50% reduction in MPN-SAF TSS from baseline to week 24 in patients with baseline TSS ≥ 10
 - Measure the change in TSS from baseline to week 12 in patients with baseline TSS ≥ 10
 - Measure the change in TSS from baseline to week 24 in patients with baseline TSS ≥ 10
 - Measure the change in TSS from baseline to time of best response in patients with baseline TSS ≥ 10
 - Measure patients' global impression of change (PGIC) at week 12
 - Measure PGIC at week 24

4.2.3 EXPLORATORY ENDPOINTS

- OS defined as time from first treatment to death due to any cause. OS of patients with MDS/MPNs and CNL is estimated between 1-3 years. OS is a standard criterion for assessing therapeutic benefit in clinical trials.
- PFS defined by Modified MDS/MPN IWG Proposed Criteria for Disease Progression in adult MDS/MPNs (Appendix H).¹ PFS is a standard criterion for assessing therapeutic benefit in clinical trials and closely correlates with OS.
- Response duration defined as time from initial response to disease progression or death.
- Correlation between the presence of specific genetic mutations as determined by next generation sequencing (NGS) and the presence or lack of a response.
- Correlation between the number of genetic mutations as determined by NGS and the presence or lack of a response.
- Correlation of clinical responses with responses of individually-matched patient-derived xenograft (PDX) mouse models. Each patient will have primary cells transplanted into a matched PDX mouse model that will, in turn, be dosed with fedratinib to assess whether PDX modeling correlates with clinical outcomes on an individual scale.
- Serial analysis of mutations at the single-cell level during treatment with fedratinib and correlation with clinical responses. Correlation of baseline c-myc staining on bone marrow core biopsy and change in c-myc staining on core biopsy and clinical response.

5 STUDY ENROLLMENT AND WITHDRAWAL

5.1 PARTICIPANT INCLUSION CRITERIA

Patients must meet all of the following criteria to be eligible for study entry:

1. Patient must understand and voluntarily sign an ICF prior to any study-related assessments/procedures being conducted
2. Be ≥ 18 years of age on day of signing informed consent.
3. Morphologically confirmed diagnosis of one of the following in accordance with WHO (2016) diagnostic criteria:
 - a. Atypical Chronic Myeloid Leukemia (aCML), BCR-ABL1 negative
 - b. Myelodysplastic/Myeloproliferative Neoplasm, Unclassifiable (MDS/MPN-U)
 - c. Myelodysplastic Syndrome/Myeloproliferative Neoplasm with ring sideroblasts and thrombocytosis (MDS/MPN-RS-T)
 - d. Chronic Neutrophilic Leukemia (CNL).
4. Palpable splenomegaly ≥ 5 cm below left costal margin (LCM), spleen volume ≥ 450 cc, AND/OR MPN-SAF TSS > 10 .
5. Patient has an Eastern Cooperative Oncology Group (ECOG) Performance Score (PS) of 0, 1 or 2
6. Able to adhere to the study visit schedule and other protocol requirements.
7. Females of childbearing potential (FCBP) must have a negative serum pregnancy test at screening. A FCBP is considered when a sexually mature female: 1) has not undergone a hysterectomy or bilateral oophorectomy; or 2) has not been naturally postmenopausal for at least 12 consecutive months.
8. A FCBP must agree to use of two methods of highly effective contraception, be surgically sterile, or abstain from heterosexual activity for the course of the study through 30 days after the last dose of study treatment.

9. Male patients must agree to use an adequate method of contraception starting with the first dose of study therapy through 90 days after the last dose of study therapy. Men must agree to not donate sperm during study therapy and for 30 days after the last dose of study therapy.

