5.2 PARTICIPANT EXCLUSION CRITERIA

Any of the following is a criterion for exclusion from the study:

1. Any of the following laboratory abnormalities:
 - a. Platelets, $< 35 \times 10^9/L$
 - b. Absolute neutrophil count (ANC) $< 1.0 \times 10^9/L$ (independent of growth factor for 7 days)
 - c. Creatinine clearance $< 30 \text{ ml/min}$
 - d. Serum amylase and lipase $> 1.5 \times \text{ULN}$
 - e. Aspartate aminotransferase (AST) or alanine aminotransferase (ALT) $> 2.5 \times \text{ULN}$,
 - f. Total bilirubin $> 1.5 \times \text{ULN}$, Patients with a total bilirubin between $1.5 - 3.0 \times \text{ULN}$ are eligible if the direct bilirubin fraction is $< 25\%$ of the total bilirubin
2. Accelerated phase or blast phase disease as defined by peripheral or bone marrow blast percentage $> 10\%$
3. Patient is pregnant or lactating female
4. Patient is a woman of childbearing potential as previously defined in inclusion #7, unless using effective contraception while on study treatment
5. Patient is a man who is a partner with of a woman of childbearing potential, unless they agree to use effective contraception while on study treatment as previously defined in inclusion #9.
6. Patient with prior history of encephalopathy, including Wernicke's Encephalopathy (WE)
7. Patient has signs or symptoms of encephalopathy, including Wernicke's Encephalopathy (e.g. severe ataxia, ocular paralysis or cerebellar signs) in which case thiamine deficiency needs to be excluded and a brain MRI might be required to exclude possible Wernicke's encephalopathy
8. Patient has thiamine deficiency if not corrected before enrollment on the study
9. Patient with concomitant treatment with or use of pharmaceutical or herbal agents known to be moderate or strong inducers of CYP3A4 or dual CYP3A4 and CYP2C19 inhibitors. For a list of moderate or strong inhibitors or inducers of CYP3A4, see table 3-2 and 3-3 at <https://www.fda.gov/drugs/drug-interactions-labeling/drug-development-and-drug-interactions-table-substrates-inhibitors-and-inducers>.
10. Patient on any chemotherapy, immunomodulatory drug therapy (e.g., lenalidomide, pomalidomide, thalidomide, interferon-alpha), ruxolitinib, anagrelide, corticosteroids $> 10 \text{ mg/day}$ prednisone or equivalent. Patients may remain on hydroxyurea (e.g., hydrea) if it is being employed to control leukocytosis as long as the patient has been on a stable dose for > 14 days prior to initiation of fedratinib.

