5.4 PARTICIPANT WITHDRAWAL OR TERMINATION

5.4.1 REASONS FOR WITHDRAWAL OR TERMINATION

Patients may withdraw consent at any time for any reason or be dropped from the trial at the discretion of the investigator should any untoward effect occur that may jeopardize participant safety. In addition, a patient may be withdrawn by the investigator if enrollment into the trial is inappropriate, the trial plan is violated, or for administrative and/or other safety reasons.

A patient must be discontinued from the trial for any of the following reasons:

- The patient or legal representative (such as a parent or legal guardian) withdraws consent
- Unacceptable adverse events
- Dose delay lasting > 12 consecutive weeks
- Intercurrent illness that prevents further administration of treatment
- Investigator's decision to withdraw the patient
- The patient has a confirmed positive serum pregnancy test
- Noncompliance with trial treatment or procedure requirements
- The patient is lost to follow-up
- Administrative reasons
- Disease progression by proposed IWG response criteria for MDS/MPN¹ (Appendix H)
- Lack of response (including clinical benefit, marrow response, partial remission, complete remission) at week 24 assessment as defined by proposed IWG response criteria for MDS/MPN¹
 - a. In cases where the investigator believes a patient is clinically deriving a benefit from fedratinib despite not meeting pre-specified criteria for clinical benefit, continuation of fedratinib will need to be approved by the study PI.
- Requiring a medication/procedure on the prohibited medication/procedure list (refer to section 7.6)
- ≥ 3 dose reductions due to AE suspected to be related to study drug

The End of Treatment and Follow-up visit procedures are listed in the Schedule of Events and Section 7.3 (Visit Requirements). After the end of treatment, each patient will be followed for 30 days for adverse event monitoring. Patients who discontinue for reasons other than progressive disease will have post-treatment follow-up for disease status and toxicity up to 30 days. Follow-up rules will apply unless participant initiates a non-study cancer treatment, withdraws consent, or becomes lost to follow-up (unsuccessful attempts to contact for 3 months). After documented disease progression, each patient will be followed 104 weeks for overall survival until death, withdrawal of consent, or the end of the study, whichever occurs first.

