6.1.7 DURATION OF THERAPY

All patients receiving at least 1 dose of study drug will be evaluable for safety and efficacy. Patients may continue on study drug until withdrawal criteria are met (section 5.4.1). Treatment duration will vary significantly between patients but is expected to average approximately 12-24 months.

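### No pregnancy test is scheduled between screening and the first dose, a gap of up to 30 days; separately, the sperm-donation ban ends 60 days before the male contraception requirement

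*Combined protocol and SAP*

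**What the plan says.** **Pregnancy testing.** Section 5.1 item 7 says that a woman of childbearing potential "must have a negative serum pregnancy test at screening". Section 7.3.1 places that serum test in a screening window of day -30 to 0, and 7.1.2 also lists it as a screening test. In the Schedule of Events (7.3.7) the pregnancy-test row has one mark, in the screening column. The Cycle 1 Day 1 list (7.3.2.1) asks staff to confirm that the patient remains eligible and to review the pregnancy-test result. It lists no new test. The same list does repeat the blood count, chemistry, amylase, lipase and thiamine.

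The related rules are these. Exclusion 3 in section 5.2 reads "Patient is pregnant or lactating female". Item 8 of 5.1 says that a woman of childbearing potential "must agree to use of two methods of highly effective contraception, be surgically sterile, or abstain from heterosexual activity", through 30 days after the last dose. Exclusion 4 bars such women "unless using effective contraception while on study treatment".

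**Male precautions.** Item 9 of 5.1 requires men to use adequate "contraception starting with the first dose of study therapy through 90 days after the last dose of study therapy". Its next sentence is "Men must agree to not donate sperm during study therapy and for 30 days after the last dose of study therapy". Exclusion 5 in 5.2 refers back to item 9 and adds no period of its own.

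**The concern.** The eligibility check on the day of dosing relies on a pregnancy result that may be a month old. A woman who became pregnant after the screening test, or whose pregnancy was too early to detect then, could pass the review at Cycle 1 Day 1 and start fedratinib. The protocol means to exclude her, and the exposure cannot be undone once the drug is given. Most of the other laboratory exclusions are checked on fresh blood that day; this one is not.

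The male point is of a different kind and weaker. Two adjacent sentences of one criterion set different end dates for precautions that appear to serve the same purpose. Contraception does not cover donation, which only the donation clause controls. Once that clause lapses, donation is open while the contraception requirement still runs.

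**Working it through.** The plan gives no figure of its own here. The check compares schedule entries and subtracts stated durations.

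**Interval from the last scheduled pregnancy test to the first dose**

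- Earliest compliant test: day -30 (7.3.1).
- Latest compliant test: day 0 (7.3.1).
- Tests listed at Cycle 1 Day 1 (7.3.2.1; 7.3.7): none, only review of the earlier result.
- Interval, taking day 0 as the day of first dose: 0 - (-30) = 30 days at most, and 0 - 0 = 0 days at least.

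This count agrees with 7.3.1, which accepts routine assessments made within 30 days of starting treatment. If day 1 is read as the day after day 0, the maximum is 1 - (-30) = 31 days. The conclusion is the same.

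**Which exclusions are re-checked on blood at Cycle 1 Day 1**

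| Exclusion (5.2) | Measure | Drawn again at Cycle 1 Day 1 (7.3.2.1)? |
|---|---|---|
| 1a, 1b | Platelets, neutrophils | Yes, blood count with differential |
| 1c | Creatinine clearance | Yes, creatinine |
| 1d | Amylase, lipase | Yes |
| 1e, 1f | AST, ALT, total bilirubin | Yes |
| 8 | Thiamine | Yes |
| 3 | Pregnancy | No, earlier result reviewed |

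**Safeguards, and whether any of them supplies a test before dosing**

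- Item 8 of 5.1: two methods, sterility or abstinence. It lowers the chance of pregnancy. It runs for the course of the study, with no stated start at consent or at first dose. It is not a test.
- Exclusion 4: tied to contraception while on treatment, so it does not clearly cover the wait before dosing. It is not a test.
- Eligibility re-check at Cycle 1 Day 1: it includes exclusion 3, but the only listed evidence is the screening result.
- Section 7.1.1: unscheduled procedures are possible if the investigator judges them clinically necessary. An early pregnancy may give no such prompt.

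**Sperm donation**

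- Contraception ends 90 days after the last dose (5.1 item 9).
- The donation ban ends 30 days after the last dose (5.1 item 9).
- Difference: 90 - 30 = 60 days, that is, days 31 to 90.

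Section 8.4.5 uses a third period, 4 months, for partner pregnancy. That is a notification window, so it does not show which precaution period is right.

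**Cost of the pre-dose test.** One assay per woman of childbearing potential. The documents do not say how many will enrol. The ceiling is the planned 25 participants: 25 x 1 = 25 assays.

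**The case against.** The strongest reply on testing is that 30 days is a maximum. A site that tests near day 0 already complies and leaves almost no gap. Item 8 can be read as binding from consent, staff must confirm eligibility on the day, and extra tests are allowed. All of this stands and makes a missed pregnancy unlikely. It does not close the gap, because nothing requires a test near the first dose.

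On donation, the reply is that this is a wording mismatch. The documents hold no male reproductive data and do not show whether 30 or 90 days is correct. That also stands, and it is why the point is minor. A reader might infer that men or their partners face a demonstrated hazard between days 31 and 90; the documents do not support that. They show only two periods in one criterion, with no reason for the difference.

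A reader might also infer that routine testing during treatment is required. Section 6.1.7 says "Treatment duration will vary significantly between patients but is expected to average approximately 12-24 months", and 5.4.1 makes it a ground for discontinuation if "The patient has a confirmed positive serum pregnancy test", yet no on-treatment test is scheduled. The documents do not carry that inference. They set no testing interval, item 8 keeps contraception in force, and 8.4.5 requires the drug to be stopped at once for a known or suspected pregnancy. Repeat testing would be a preference, and 12-24 months is an expected average that cannot bound the number of tests for one woman.

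**Conclusion.** Both points hold, with different weight.

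The missing pre-dose test is the main one. Up to 30 days can separate the only scheduled pregnancy test from the first dose, and no listed safeguard supplies a later result. The probability of a missed pregnancy is low and cannot be sized, because the number of women of childbearing potential is not given. The change is justified because the exposure would be irreversible and the remedy costs little.

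The donation clause is a minor internal inconsistency of 60 days. It is not evidence of harm.

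The conclusions rest on reading the single mark in the 7.3.7 row as complete, which 7.3.1 and 7.3.2.1 support, and on taking day 0 as the day of first dose. Sample size, error rates, the interim rule and the efficacy analyses are unaffected.

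**What to change.** 1. In 7.3.2.1 and the 7.3.7 table, add a serum pregnancy test for women of childbearing potential at Cycle 1 Day 1, taken on the existing blood draw, with a negative result known before fedratinib is given. Keep the screening test.
2. In 5.1 item 9, change the sperm-donation ban from 30 to 90 days after the last dose, to match the contraception period in the same criterion.

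The cost is a short amendment with matching consent wording and one assay per woman of childbearing potential. No visit or extra draw is added. The one practical burden is that her first dose waits for the result.
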